**Visit Frequency:**

Consented Participants will be seen and evaluated for enrollment during Screening (up to 30 days prior to Baseline, Day 0). There are 10 Visits during the study from Day 0 to Day 180 for Study Injections and follow-up.

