**FOOTNOTES FOR THE SCHEDULE OF ACTIVITIES**

**Note:** The Schedule of Activities includes activities during Screening and all Study Visits.

**Order of Assessments during Visits (if assessment is to be performed):** AEs/TEAEs, vital signs and weight, ALSFRS-R, HHD, ATLIS, pregnancy test, complete physical exam, SVC, ALSAQ-40, other questionnaires (PGIC and CGIC), blood sample collection for laboratory assessments, and muscle biopsy

- a Day 0 is the Baseline Visit
- b The Day 14 Visit will be scheduled 13-15 days after the Day 0 Visit, the Day 74 Visit will be scheduled 13-15 days after the Day 60 Visit, and the Day 134 Visit will be scheduled 13-15 days after the Day 120 Visit
- c Muscle biopsies will be collected as the last procedure of the Visit. It is collected predose on Day 0.
- d Day 84 muscle biopsy is optional.

**Abbreviations:** AEs = adverse events; AESI = adverse events of special interest; ALSFRS-R = Revised Amyotrophic Lateral Sclerosis Functional Rating Scale; ALSAQ-40 = Amyotrophic Lateral Sclerosis Assessment Questionnaire, 40 questions; ATLIS = accurate test of limb isometric strength; CGIC = Clinical Global Impression of Change; D = day; ET = early termination or withdrawal; HHD = Handheld Dynamometry; PGIC = Patient Global Impression of Change; SVC = Slow Vital Capacity; TEAEs = treatment-emergent adverse events; TESAEs = treatment-emergent serious adverse events

1. **Informed Consent** process is to be completed at Screening prior to conducting any study-specific procedures.
2. **Demographics and Baseline Characteristics** will include age, gender, race, and ethnicity and will be collected at Screening.
3. **Medical History and Familial Cancer History:** A medical history and familial cancer history will be obtained at Screening. The Investigator will confirm the diagnosis of ALS using the revised El Escorial / Airlie House diagnostic criteria. Participants will be confirmed as having clinically definite ALS, clinically probable ALS, or clinically probable laboratory-supported ALS  $\leq 4$  years.

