24. **AESI: Injection Site Reactions (ISRs)** must be initially assessed immediately after all injections at an Injection Visit. The Investigator or designee will follow up with the Participant within 2 to 3 days after Study Injections to ask the Participant about reactions at any injection sites and, if any are noted, the worst reaction will be recorded as a TEAE and considered an AESI.

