## 4. STUDY DESIGN

### 4.1. Overall Design

VMALS-002-2 is a Phase 2a, double-blind, randomized, placebo-controlled, multicenter study designed to assess the safety of IM administration of Engensis in Participants with ALS as compared to Placebo. Study Participants will be randomized in a 2:1 ratio to Engensis or Placebo (control group). The study will include only patients with limb onset of ALS.

**Screening.** Screening activities (see SoA, Section 1.3) include assessments to determine study eligibility, assessments to establish Baseline results for use in analysis of endpoints, and Baseline safety assessments. All Screening activities will occur within the 30 days prior to Day 0.

**Randomization.** Participants who meet the eligibility criteria will be randomly assigned in a 2:1 ratio to one of the two treatment arms, Engensis or Placebo. Randomized treatment assignment will occur through the EDC randomization module in a double-blinded fashion. Blinding will be achieved by having the study medication (Engensis and Placebo) prepared by the unblinded Pharmacist or delegated staff.

**Treatment Period.** Participants will undergo three Treatment Cycles of Study Injections (Engensis or Placebo) at 60-day intervals (on Days 0 and 14, Days 60 and 74, and Days 120 and 134), with follow-up Visits at Days 30, 84, 144, and 180/ET.

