**4.4. Justification for Dose**

Pharmacokinetic studies in animals and humans both indicate that VM202 (Engensis) has very limited systemic distribution. The plasmid DNA product is taken up into muscle cells within a radius of about 1 cm of each IM injection site. Only a small fraction of VM202 DNA is detectable in the systemic circulation following IM injection. VM202's short circulatory half is 2 to 5 minutes consequent to rapid clearance by circulating DNases and rapid uptake by the liver (reference Investigator's Brochure). The expression of human HGF after intracellular VM202 uptake continues for about 2 to 3 weeks following injection (*ibid.*). As HGF protein can bind to heparan sulfate, which is abundant in the extracellular matrix (ECM), longer-term retention of HGF protein results from entrapment within the ECM. Most HGF released into circulation, including from the ECM, is quickly degraded. The repeated injection of Engensis in study VMALS-002-2, with 6 treatment days over 19 weeks, is thus expected to provide enhanced HGF expression for approximately 5 to 6 months.

In addition, the favorable safety profile of Engensis from 10 clinical studies with over 500 total Participants who have received the drug indicates that the minimal safety risk of 3 cycles of treatment with Engensis over a 19-week period is justified for Participants with a life-threatening illness who may receive a potential benefit from increased neuromuscular activity and greater ability to exert self-control of voluntary muscle movements during their participation in study VMALS-002-2.

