### **8.5.2. Method of Detecting AEs, TEAEs, SAEs and TESAEs**

The method of recording, evaluating, and assessing causality of AEs, TEAEs, SAEs and TESAEs, and the procedures for completing and transmitting SAE reports are provided in Section 10.2, Appendix 2.

Care will be taken not to introduce bias when detecting AEs and/or SAEs. Open-ended and non-leading verbal questioning of the Participant is the preferred method to inquire about AE occurrences.

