#### **8.5.4.3. Injection Site Reactions**

The most common ISRs in the prior Phase 1/2 study in ALS Participants were local pain and bruising at the site of injection. A follow-up notification for ISRs will occur within 2 to 3 days after each Study Injection Visit. The location and temporal relationship to the most recent injections will determine whether the event is an ISR and should be reported as a TEAE. For an AE to qualify as an ISR, the reaction must be located in close proximity to an injection site and be first observed and graded within 48 hours following Study Injections. ISRs that remain unresolved after 48 hours will continue to be assessed at subsequent Visits as ongoing AEs until resolved.

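### The 2 to 3 day contact after each injection visit is specified only as an injection-site inquiry; one added open question would bring the first scheduled general adverse event inquiry forward from a nominal 10 to 16 days.

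*Protocol*

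**What the plan says.** **The contact.** Protocol Section 1.3, footnote 24, requires an injection-site check straight after the injections. It then tells the investigator or designee to "follow up with the Participant within 2 to 3 days after Study Injections to ask the Participant about reactions at any injection sites", with the worst reaction recorded as a TEAE. Section 8.5.4.3 puts it this way: "A follow-up notification for ISRs will occur within 2 to 3 days after each Study Injection Visit". Neither place mentions a general AE question.

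**The visits.** Section 4.1 places injections "on Days 0 and 14, Days 60 and 74, and Days 120 and 134", "with follow-up Visits at Days 30, 84, 144, and 180/ET". AE/TEAE recording is the first item in the order of assessments at visits (notes to the Schedule of Activities).

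**General AE collection.** Footnote 22 and Section 8.5.1 collect TEAEs from the first injections to Day 180. On method, Section 8.5.2 says: "Open-ended and non-leading verbal questioning of the Participant is the preferred method to inquire about AE occurrences". It sets no time for the questioning. Footnote 23 calls for continuous monitoring of AEs of special interest but gives no mechanism. Section 8.5.5 covers follow-up of events already reported. SAP Section 6.14.1 repeats the collection period and adds no contact. Neither document describes an AE diary or a separate AE call.

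**The endpoint.** The first primary endpoint (Protocol Section 9.3.1) is the incidence of all TEAEs and serious TEAEs against Placebo, summarised without formal testing or imputation.

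**The concern.** Safety is the sole primary objective, and the first primary endpoint counts every TEAE, local or not. As written, local reactions are actively asked about at 2 to 3 days. A short-lived non-local complaint in the same days, such as a day of feverishness or headache, has no scheduled inquiry until the next visit. By then it may be forgotten, or remembered without a clear onset date.

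Onset dates matter here. Causality assessment uses the temporal relationship to the study intervention (Protocol Appendix 2), and SAP Section 6.2.5 imputes a start date with a missing day as the first of the month, or as the first dose date if that falls in the same month.

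With 12 and 6 participants planned, one participant is 1/12 = 8 percentage points of incidence on Engensis and 1/6 = 17 points on Placebo. A few unrecorded events can visibly change a descriptive table.

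**Working it through.** **1. Check the visit list against the plan's own figures.** Six injection days plus Days 30, 84, 144 and 180 give 0, 14, 30, 60, 74, 84, 120, 134, 144, 180: ten visits. This agrees with the synopsis: "There are 10 Visits during the study from Day 0 to Day 180 for Study Injections and follow-up". Footnote 21 puts Days 84 and 144 about 10 days after the preceding injections; 84 − 74 = 10 and 144 − 134 = 10.

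**2. Gap from each injection visit to the next scheduled visit.** Nominal gap = next visit day − injection day. For the windows, Days 30, 60, 84, 120 and 144 each carry ±3 days, taken here as counted from Day 0. The second injection visit of each cycle falls 13 to 15 days after the first (for Cycle 1: "The Day 14 Visit will be scheduled 13-15 days after the Day 0 Visit").

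| Injection visit | Next visit | Nominal gap (days) | Gap with windows (days) |
|---|---|---|---|
| Day 0 | Day 14 | 14 | 13 to 15 |
| Day 14 | Day 30 | 16 | 27 − 15 = 12 to 33 − 13 = 20 |
| Day 60 | Day 74 | 14 | 13 to 15 |
| Day 74 | Day 84 | 10 | 81 − (63 + 15) = 3 to 87 − (57 + 13) = 17 |
| Day 120 | Day 134 | 14 | 13 to 15 |
| Day 134 | Day 144 | 10 | 141 − (123 + 15) = 3 to 147 − (117 + 13) = 17 |

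The nominal range is 10 to 16 days and the permitted range 3 to 20 days. An event arising 1 to 3 days after injection is first asked about, on nominal days, between 10 − 3 = 7 and 16 − 1 = 15 days after it occurs.

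**3. Number of contacts.** 6 injection visits × 18 participants = 108 planned contacts, if everyone attends all six.

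**4. Effect of equal loss in both arms.** If a fraction L of affected participants goes unrecorded in each arm, observed incidence is p(1 − L). The difference becomes (p1 − p0)(1 − L), and the ratio stays p1/p0. Illustration with assumed rates only: p1 = 50%, p0 = 16.7%, true difference 33.3 points, ratio 3.0.

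| L (assumed) | Observed difference | Observed ratio |
|---|---|---|
| 20% | 33.3 × 0.8 = 26.7 points | 3.0 |
| 50% | 33.3 × 0.5 = 16.7 points | 3.0 |
| 60% | 33.3 × 0.4 = 13.3 points | 3.0 |

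**5. Chance of recording at least one affected participant among 12 on Engensis.** 1 − (1 − p·s)^12, where s is the share recalled. Both p and s are assumptions.

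| True rate p | s = 100% | s = 80% | s = 50% | s = 30% |
|---|---|---|---|---|
| 20% | 93% | 88% | 72% | 52% |
| 10% | 72% | 63% | 46% | 31% |

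Tables 4 and 5 show how such loss would act. They do not estimate it; the documents give neither event rates for such complaints nor recall rates.

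**The case against.** **Silence is not prohibition.** Footnote 24 belongs to the injection-site row, so it naturally describes that task. TEAEs are collected throughout the study, and nothing stops a site from asking more or from recording what a participant volunteers. The Study Drug Injection Guidelines, which are not among the documents, may hold a wider script. This stands: the point is about what is scheduled, and a reader should not infer that other events are barred from the contact.

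**No conflict with Section 8.5.2.** A reader might infer that a directed question departs from that section. It does not. The section states a preference, and targeted questioning about a pre-specified event of special interest can coexist with it.

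**The known profile is local.** A reader might infer that, with needle trauma equal in the two arms, a drug effect would more likely appear in non-local events. The documents do not support this. Section 4.4 reports very limited systemic distribution and uptake within about 1 cm of each injection site. Sections 2.2 and 2.3.1 attribute no systemic effects to Engensis and report mainly injection-site events. In the earlier ALS study only injection-site reactions were considered related to treatment (Synopsis). Equal needle trauma also leaves room for a local effect of the product. Nor does the expression period single out Day 2 to 3: "The expression of human HGF after intracellular VM202 uptake continues for about 2 to 3 weeks following injection", so visits at 10 to 16 days fall within or near that period too.

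**Other ascertainment exists.** Temperature and other vital signs are taken about 2 hours after dosing. Table 6 grades widespread skin reactions, bronchospasm, anaphylaxis and hypotension. Concomitant medications, with indication and start date, are reviewed at every visit and may prompt recall of a treated complaint. Serious events must be reported within 24 hours of site awareness. This stands and narrows the gap, though none of it is a general question in the days after injection.

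**Overall incidence may barely move.** AEs occurred in 17 of 18 participants (94.4%) in the earlier ALS study, so the any-TEAE rate may be near its ceiling. A reaction recurring after three visits, each with an independent 50% chance of being forgotten, would be missed entirely only 0.5³ = 12.5% of the time. Both are fair. Any effect would show more in individual preferred terms and onset dates than in the any-TEAE row.

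**Conclusion.** The point holds as a gap in scheduled ascertainment. In the protocol and SAP as written, the first general AE inquiry after each of the six injection visits comes nominally 10 to 16 days later (3 to 20 with windows), although a contact limited to injection sites takes place at 2 to 3 days. The consequence is confined mainly to mild, transient, non-local, non-serious TEAEs, which may be under-counted or imprecisely dated in both arms.

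A reader might infer a bias in the treatment comparison. The schedule is the same in both blinded arms. If loss is equal, the absolute difference shrinks and the risk ratio is unchanged; nothing in the documents indicates unequal loss. The amount lost cannot be estimated from them.

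This is a cheap improvement to the sole primary objective, not a defect that undermines the trial. It assumes that no wider script exists in the Injection Guidelines. If one does, the protocol need only say so.

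**What to change.** Reword footnote 24 and Section 8.5.4.3 so that the existing 2 to 3 day contact:

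1. first asks one open-ended question about any new or worsened health problem since the injections, in line with the preference in Section 8.5.2;
2. records any qualifying answer as a TEAE, with its onset date;
3. then asks about the injection sites as now;
4. uses the same script for every participant.

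This moves the first scheduled general AE inquiry from a nominal 10 to 16 days to 2 to 3 days after each injection visit. It needs no extra visit: one more question in contacts already planned (108 at full attendance) and a wording change in two places. The downside is slightly more mild TEAEs recorded in both arms.

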**10.3. Appendix 3. Grading of Injection Site Reactions**

The following grading guidelines were compiled from sources from the FDA and the National Cancer Institute for Injection Site Reactions (Table 6). Injection sites should be assessed in each upper and each lower limb. A global assessment of all injection sites on each arm and on each leg is to be performed following each treatment. The injection site reaction with the most severe pain/tenderness, erythema/itching/urticaria, and bruising/swelling/bleeding on each arm and on each leg is to be used as the reference point for the injection site reaction grading following each treatment. Note that the most severe pain/tenderness injection site may not be the same injection site reaction with the most severe bruising/swelling/bleeding.

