**Table 6: Injection Site Reaction Grading**

Reaction at Injection Site a	Mild (Grade 1)	Moderate (Grade 2)	Severe (Grade 3)	Potentially Life-Threatening (Grade 4)
Pain, tenderness	Mild discomfort to touch, with or without warmth, erythema, itching	Symptoms with or without swelling and/or phlebitis	Symptoms with or without swelling or phlebitis or mild infection	Symptoms with severe infection or tissue injury or ulceration
	Does not interfere with daily activity	Interferes with daily activity	Precludes daily activity	Requires advanced medical and/or surgical care, including intravenous (IV) medications
	No or local treatment	Use of non-narcotic pain reliever	Use of narcotic pain reliever and/or oral antibiotics	
Erythema, itching, urticaria	Mild, localized itching, erythema or urticaria	Symptoms with skin changes beyond local injection site(s)	Symptoms with widespread skin changes	Bronchospasm, anaphylactoid, or anaphylactic reaction
	Does not interfere with activity	Interferes with movement and daily activity	Interferes with daily activity	Requires advanced medical care, including IV medication
	Use of topical treatment	Use of NSAIDs and/or antihistamines	Use of oral steroids or immuno-suppressives	
Bruising, swelling, bleeding	Mild, localized swelling, ecchymosis or hematoma	Moderate ecchymosis or hematoma	Extensive ecchymoses, large hematoma	Hypotension, life-threatening consequences
	Does not interfere with activity	Interferes with daily activity	Precludes activity	Requires transfusion, urgent intervention
	No treatment	Requires leg elevation, conservative treatment	Requires minimally invasive drainage	

Abbreviations: NSAID = non-steroidal anti-inflammatory drugs

a Injection site reactions are a category of AESIs and should be recorded as AEs using these grading guidelines.

---

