The following tables will be presented:

- Summary of TEAE (Table 14.3.1.1)

QMD Ref: Worldwide-TMP-ST-005-7.0 Effective: 12Aug2019	Governing QMD: Worldwide-SOP-ST-001
Confidentiality Statement	

This document is the property of Worldwide Clinical Trials Inc. and may not be duplicated, copied, altered or removed from company without prior approval from Worldwide Quality Assurance or in compliance with Worldwide Standard Operating Procedures.

Worldwide Clinical Trials Controlled Quality Management Document			
 WORLDWIDE CLINICAL TRIALS	Sponsor:	Helixmith Co., Ltd.	
	Protocol Number:	VMALS-002-2	
STATISTICAL ANALYSIS PLAN VERSION 3.0			

- TEAEs organized by SOC and PT (Table 14.3.1.2)
- TESAEs organized by SOC and PT (Table 14.3.1.3)
- TEAEs organized by SOC and PT and Maximum Severity (Table 14.3.1.4)
- TEAEs organized by SOC and PT and Maximum Relationship (Table 14.3.1.5)
- TESAEs organized by SOC and PT and Maximum Severity (Table 14.3.1.6)
- TESAEs organized by SOC and PT and Maximum Relationship (Table 14.3.1.7)
- Incidence Injection site reactions by SOC and PT (Table 14.3.1.8)
- Incidence of clinically significant laboratory values (Table 14.3.1.9)
- AESIs organized by SOC and (Table 14.3.1.10)
- TEAEs leading to study discontinuation by SOC and PT (Table 14.3.1.11)
- TESAEs leading to study discontinuation by SOC and PT (Table 14.3.1.12)
- TEAEs leading to study drug withdrawal by SOC and PT (Table 14.3.1.13)
- TESAEs leading to study drug withdrawal by SOC and PT (Table 14.3.1.14)
- TEAEs related to study medication by SOC and PT (Table 14.3.1.15)
- TESAEs related to study medication by SOC and PT (Table 14.3.1.16)

The following listings will be provided:

- All AEs (Listing 16.2.7.1)
- AESIs (Listing 16.2.7.2)
- TESAEs (Listing 16.2.7.3)
- Injection Site Reactions (Listing 16.2.7.4)
- TEAEs leading to study discontinuation (Listing 16.2.7.5)
- TEAEs related to study medication (Listing 16.2.7.6)
- TESAEs leading to death (Listing 16.2.7.7)

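### Footnote 24 keeps only the worst injection site reaction, so if sites follow it the by-preferred-term incidence in Table 14.3.1.8 is understated for the less dominant reaction types

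*Protocol*

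**What the plan says.** ISR incidence by arm is one of the three primary endpoints (Protocol Section 9.3.1, SAP Section 3.1). Four Protocol texts bear on how an ISR becomes a record.

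- Schedule of Activities, footnote 24. Sites are assessed immediately after the injections and the participant is contacted 2 to 3 days later. Then, where the participant reports reactions, "the worst reaction will be recorded as a TEAE and considered an AESI".
- Appendix 3 (Section 10.3). The assessment unit is the limb: "A global assessment of all injection sites on each arm and on each leg is to be performed following each treatment". The reference for grading is taken type by type: "The injection site reaction with the most severe pain/tenderness, erythema/itching/urticaria, and bruising/swelling/bleeding on each arm and on each leg is to be used". It adds: "Note that the most severe pain/tenderness injection site may not be the same injection site reaction with the most severe bruising/swelling/bleeding".
- Table 6 footnote: "Injection site reactions are a category of AESIs and should be recorded as AEs using these grading guidelines".
- Section 8.5.4.3: "The location and temporal relationship to the most recent injections will determine whether the event is an ISR and should be reported as a TEAE".

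On the analysis side, SAP Section 6.14.1 plans "Incidence Injection site reactions by SOC and PT (Table 14.3.1.8". The SAP has no rule for ranking or collapsing several reactions at one visit, and this table has no breakdown by Table 6 grade.

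**The concern.** Footnote 24 speaks of one reaction, the worst. The other three texts treat pain, erythema and bruising as separate reactions and limit recording only by location and timing. No text says which governs, or how to choose the worst among reactions of different types but equal grade.

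If a participant has pain and bruising after the same visit and the site records only the pain, the bruising never reaches its preferred-term row. The loss is therefore one of participants within a row, and not only of repeat events. It falls on the types that tend to rank behind another. If the dominant type is more frequent in one arm, more of the other types are hidden in that arm, so the arm contrast by type can move even when every site applies the same rule.

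**Working it through.** **What differs.** Appendix 3 has 3 types × 4 limbs = 12 graded cells per Injection Visit. Limbs do not affect participant-level incidence, because a participant counts once per preferred term however many limbs are involved. Only the three types matter here.

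**Inputs from the documents.** Six Injection Visits (Days 0, 14, 60, 74, 120 and 134; Section 4.1); 12 Engensis and 6 Placebo participants (Section 5.3); three reaction types (Table 6). The plan states no ISR rate by type and no precision figure, and Section 9.3.1 rules out formal testing of safety, so there is no planned figure to reproduce.

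**Assumptions, not in the documents.** Per-visit probabilities p (pain), e (erythema) and b (bruising), independent across types and visits. All reactions have the same grade, so the worst is chosen either at random or in the fixed order pain, bruising, erythema. One follow-up per Injection Visit.

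**Formulas.** If r is the per-visit probability that a type is recorded, six-visit participant incidence is 1 − (1 − r)^6.

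- Every type recorded: r = p, e or b.
- Worst only, fixed order: pain p; bruising b(1 − p); erythema e(1 − p)(1 − b).
- Worst only, random tie-break: the type's own rate × [P(neither other type) + P(exactly one other)/2 + P(both others)/3].

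Example, bruising at 0.3/0.1/0.2: every type recorded, 1 − 0.8^6 = 73.8%. Fixed order, r = 0.2 × 0.7 = 0.14, giving 1 − 0.86^6 = 59.5%. Random, r = 0.2 × [0.63 + 0.34/2 + 0.03/3] = 0.162, giving 1 − 0.838^6 = 65.4%.

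| Per-visit rates (pain/erythema/bruising) | Rule | Pain | Erythema | Bruising | Any ISR |
|---|---|---|---|---|---|
| 0.1/0.05/0.1 | every type | 46.9% | 26.5% | 46.9% | 79.2% |
| | worst only, random | 44.2% | 24.2% | 44.2% | 79.2% |
| | worst only, fixed | 46.9% | 22.0% | 43.2% | 79.2% |
| 0.3/0.1/0.2 | every type | 88.2% | 46.9% | 73.8% | 98.4% |
| | worst only, random | 83.2% | 38.2% | 65.4% | 98.4% |
| | worst only, fixed | 88.2% | 29.2% | 59.5% | 98.4% |

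At the low rates the affected types lose 2.3 to 4.5 points; at the middle rates, 5.0 to 17.7. Pain loses nothing when it always ranks first. In 12 Engensis participants at the middle rates, expected erythema falls from 5.6 participants to 4.6 or 3.5.

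**Effect on the arm contrast.** Assume bruising of 0.2 per visit in both arms, pain of 0.3 in one arm and 0.1 in the other, and pain ranked first. True six-visit bruising is 1 − 0.8^6 = 74% in both. Recorded bruising is 1 − (1 − 0.2 × 0.7)^6 = 60% in the first arm and 1 − (1 − 0.2 × 0.9)^6 = 70% in the second.

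**Plausibility of the rates.** The earlier ALS study had 26 Grade 1 ISRs (Synopsis) in 18 participants over four visits (Section 2.2.6.1): 26/(18 × 4) = 0.36 per participant-visit. This lies between the summed rates of the two scenarios, 0.25 and 0.60. How that study recorded ISRs is not stated, and it gave 64 injections per visit against 128 here (Section 4.4.2).

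**The case against.** The strongest reply is that footnote 24 is one loosely worded note against three other texts. Its worst-only clause follows the contact at 2 to 3 days and need not cap what is recorded at the immediate assessment. It could also mean the worst over the 128 sites, with Appendix 3 supplying the split by type and limb. Footnote 22 separately requires adverse events after the first injection to be recorded. The eCRF and the injection guidelines, which may settle the matter, are not available here. All of this is fair, but footnote 24 does not say any of it, so a site can reasonably follow it as written.

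The reply is also right that the overall endpoint is untouched. A reader might infer that the headline ISR incidence is wrong. It is not: at least one reaction is recorded under either rule.

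A reader might set six records per participant against 72 (12 cells × 6 visits). That compares adverse event records with graded cells. Appendix 3 is mainly a grading instruction and never asks for 12 adverse event records per visit.

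A reader might also infer that the arms become incomparable. The documents do not show this: site staff are blinded (Section 6.3.2) and both arms share the same text. Masking can distort a contrast by type, but only if the rate of the dominant type differs between arms.

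On grade, ISRs do enter Table 14.3.1.4 by maximum severity and have their own Listing 16.2.7.4. But the general intensity scale in Section 10.2.5 has three levels and Table 6 has four type-specific grades, so part of the grade information still has no table.

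**Conclusion.** The texts conflict and should be reconciled. Any-ISR incidence does not depend on the choice. Incidence by preferred term does: under literal use of footnote 24 it is too low for the types that rank behind another. The loss is about 2 to 5 points at low assumed rates and about 5 to 18 at middle rates, over six visits.

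These sizes rest on independence between types, equal grades and the two tie-break rules. At the low rates the shift is under one participant in 12. Section 2.2 reports injection site pain in only 1-4% of participants across earlier studies, which points to a small effect. A much larger loss can be produced, for example bruising falling from 60% to 0.60 × (1 − 0.80) = 12% at one visit with pain in 80% and always ranked first, but the documents give no support for rates that high. This is a modest defect in a primary-endpoint display that is cheap to remove.

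**What to change.** Reword footnote 24 to match Appendix 3: at each Injection Visit, the worst grade of each of the three reaction types is recorded as its own ISR. Keep limb as an attribute of the record, not as a separate adverse event; splitting by limb would raise event counts without changing participant-level incidence. Carry the same rule into the eCRF guidance.

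In the SAP, have Table 14.3.1.8 report the number and percentage of participants by reaction type and maximum Table 6 grade, each participant counted once per type. Reporting by reaction type matters because each Table 6 row groups several terms, so preferred-term rows alone would still depend on which term the site entered. A breakdown by cycle is optional.

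The cost is footnote and eCRF wording, somewhat more ISR records and a few more table rows. Appendix 3 already requires the grades.
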